9.9. Sample Handling

9.9.1. Sample handling for trial purposes

Participants will have blood drawn at their screening visit. This will involve a 5ml (one teaspoonful) blood sample for HbA1c level which will be analysed in the OUH NHS Trust laboratory and destroyed once the sample has been analysed. At visits 1, 2, 3 and 4 participants will have further blood tests taking a maximum of 35ml (around two tablespoonsful) of blood on each occasion. Some of these will be sent to the OUH NHS Trust laboratory for glucose levels, insulin levels, fructosamine levels, full blood count, lipid profile, urea, creatinine and electrolytes. Samples handled by the NHS laboratory will be disposed of after analysis. In addition, plasma and serum will be spun in ORTU's research lab and stored as described below.

9.9.2. Sample handling for long term storage

Plasma and serum samples will be collected at visits 1, 2, 3, and 4. These will be spun, and plasma/serum will be aliquoted for storage in a -80°C freezer. These samples will be stored long-term for use in future ethically approved studies. Consent for this long term sample storage will be sought from participants.

9.10. Early Discontinuation/Withdrawal of Participants

Participants can withdraw at any time without giving a reason and without affecting their quality of future medical care. This may happen for a number of reasons, including but not limited to:

- The occurrence of what the participant perceives as an intolerable AE.
- Inability to comply with trial procedures
- Participant decision

Consent can be withdrawn at three levels:

No further contact – means that the research team no longer contacts the patient directly, but still has their permission to use information, samples and to obtain further information from health records.

No further access – means that the research team no longer contacts the patient or obtains information from their health records, but still has permission to use the information and samples already collected.

No further use — means that the research team no longer contacts the patient or obtains further information, and aims to destroy all samples already collected (though tracing previously distributed samples may not always be possible). Data already entered on to the database cannot be deleted.

In addition, the Investigator may discontinue a participant from the trial treatment at any time if the Investigator considers it necessary for any reason including, but not limited to:

- Ineligibility (either arising during the trial or retrospectively having been overlooked at screening)
- Significant protocol deviation
- Significant non-compliance with treatment regimen or trial requirements
- An adverse event which requires discontinuation of the trial medication or results in inability to continue to comply with trial procedures
- Disease progression which requires discontinuation of the trial medication or results in inability to continue to comply with trial procedures

The reason for withdrawal, if known, will be recorded in the CRF. If the participant is withdrawn due to an adverse event, the investigator will arrange for visits or telephone calls to collect follow-up information on the adverse event until the adverse event has resolved or stabilised. Withdrawals/discontinuations will be replaced to ensure that the appropriate number of participants completing the trial as per protocol.

9.11. Definition of End of Study

The end of study is defined as the last visit of the last patient undergoing the study follow-up and when all the samples have been analysed.

10. SAFETY REPORTING

Safety data will be collected as described below for serious adverse events that occur from the participant's Screening Visit until their Visit 4.

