7. STUDY DESIGN

The study is a single tertiary-centre, crossover, randomised controlled trial to evaluate the effects of CPAP withdrawal versus continued CPAP on overnight interstitial glucose levels and other measures of cardiovascular risk, OSA severity, and daytime symptoms in patients with CPAP-treated obstructive sleep apnoea and T2DM (not on insulin therapy) or "prediabetes", following withdrawal of CPAP for 7 days.

Data will be collected using a continuous glucose monitor which is a semi-invasive way of monitoring interstitial glucose levels at home over the whole of the day and night up to a maximum period of 10 days. This method of monitoring glucose levels has been chosen because it allows monitoring of overnight glucose levels in a "real-world" setting. Alternative means of monitoring overnight glucose levels would

require hospital admission, intravenous cannulation and frequent blood draws during sleep. In addition, overnight oximetry will be measured at home along with other markers of cardiovascular disease. A blood test will be taken at the screening visit to screen for the presence of undiagnosed diabetes. Further blood tests will be taken at visits 1, 2, 3 and 4 to measure fasting glucose and insulin levels to establish if CPAP withdrawal affects these measures. Subjective sleepiness will be recorded by a questionnaire at screening and visits 1, 2, 3, and 4.

The trial consists of a consent visit which will also be the screening visit, a randomisation visit which also forms the first study visit (visit 1) and three subsequent trial visits following randomisation (visits 2, 3, and 4). Screening consists of one week of pulse oximetry while on CPAP for 3 nights and off CPAP for 4 nights. Following screening, there will be at least 14 days, and no more than 12 weeks, back on CPAP prior to the randomisation visit. Following the randomisation visit participants will then use either sham CPAP or continued therapeutic CPAP for 7 days. They will be placed back onto their own CPAP for at least 14 nights before crossing over. There will be four study visits within 18 weeks of the start of screening. Details of the study visits are shown below in the study flow diagram:

Study flow diagram. CGM=Continuous glucose monitoring, CPAP=continuous positive airway pressure, ESS=Epworth sleepiness score,

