9.3. Screening and Eligibility Assessment

Potentially eligible participants that are interested will be invited to meet with the research team on a screening visit. Exclusion and inclusion criteria will be reviewed and informed consent will be obtained prior to any trial specific procedures as described above. Participants will then undergo ambulatory nocturnal pulse oximetry for 7 nights. The first three nights are carried out on the participants' normal CPAP therapy to confirm adequate control with an ODI < 10 events/ hour. The participant is then taken off CPAP therapy for 4 nights with oximetry monitoring on all four nights. A return of > 20/h oxygen desaturations (≥4% dips) on any of the 4 nights confirms that sufficiently severe OSA has returned to satisfy the entry criteria. Manual editing for clear awake periods or clear periods of artefact will be allowed at the discretion of the investigator.

The initial phase of the study where CPAP is withdrawn for 4 nights provides additional interesting data, as not all patients do experience a return of OSA in that time period. Those that do not experience a return

of OSA do not enter the main study, however this data will be retained to try and understand why some patients relapse quickly on withdrawal and others do not.

At the screening visit, participants will have a blood test to measure HbA1c levels to confirm eligibility (HbA1c ≥6.0% (42mmol/l) at screening visit). This procedure is described in more detail later. Participants will not need to be fasted prior to this assessment. Participants will be contacted by telephone prior to stopping their CPAP therapy if they are not eligible on the basis of their HbA1c. Data from the first three nights of oximetry recordings on CPAP will provide useful clinical data ensuring they are on the correct CPAP settings. Data from these recordings will be passed on to the clinical team for onwards clinical care.

Following the screening week eligible participants resume their CPAP therapy for at least 14 days and no more than 12 weeks prior to randomisation. Participants eligible for entry into the study will then be contacted by the research team to arrange randomisation and subsequent study visits.

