9.8. Subsequent Visits

The assessments at these visits will be identical to the baseline assessments at Visit 1 described in Section 9.6 aside from the following assessments.

Participants will attend Visit 2 seven days after Visit 1, and Visit 4 seven days after Visit 3. Following Visit 2 participants will return to using their own CPAP machine for at least 14 days prior to returning for Visit 3.

CGM and oximetry data will be downloaded at visits 2 and 4. At Visit 3 participants will be supplied with a continuous glucose monitor (Dexcom G6®) as described in Section 9.6.

Data from participants CPAP machine will be downloaded for an average use of CPAP over all intervention days at Visits 2 and 4. At visit 3 data from participants' CPAP machine will be downloaded for an average use of CPAP over all days in the last 14 days prior to visit. This will not be assessed as an eligibility criterion as this will have already been assessed at the screening visit.

At visits 2 and 4 participants will have their own CPAP machine returned and will be instructed to restart using this from the night following this visit. At Visit 3 participants will then be supplied with a new CPAP machine, either therapeutic or sham. The participant's own CPAP machine will be collected and securely stored until Visit 4.

At the end of study visit 4 the participants will be asked to return all study equipment and participants' involvement in the study will end.

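### SAE collection stops at Visit 4, so the CPAP-first sequence has no observation after the sham week (sham-first has at least 21 days), and exposed screen failures and early stoppers have no defined end

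*Protocol*

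**What the plan says.** Section 10 defines the safety window as "serious adverse events that occur from the participant's Screening Visit until their Visit 4". Section 9.8 fixes the calendar around that visit: "Participants will attend Visit 2 seven days after Visit 1, and Visit 4 seven days after Visit 3". Between the two treatment periods, "Following Visit 2 participants will return to using their own CPAP machine for at least 14 days prior to returning for Visit 3". At Visits 2 and 4 the participant's own machine is handed back and participants "will be instructed to restart using this from the night following this visit". Section 9.8 then closes the trial for the individual: "At the end of study visit 4 the participants will be asked to return all study equipment and participants' involvement in the study will end". Section 7 sets the outer limit: "There will be four study visits within 18 weeks of the start of screening".

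Section 9.3 takes every potential participant who passes the HbA1c check off CPAP for four nights before randomisation. It refers to "Those that do not experience a return" of OSA, and says that they do not enter the main study. Section 9.10 arranges contact until an adverse event resolves or stabilises, but only for participants withdrawn because of that event. Section 10.4 provides for follow-up or corrected information on SAEs already reported.

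**The concern.** The intervention under study is withdrawal of CPAP, so one would expect the safety window to be set by when withdrawal ends. Instead it is set by a visit whose distance from withdrawal depends on the randomised order. In one sequence the visit comes three weeks or more after the sham week. In the other it coincides with the end of the sham week, before effective treatment has resumed.

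The protocol itself shows why the hours and days just after the sham week matter. Section 16.4 names daytime sleepiness as the main effect of withdrawal and advises participants not to drive if sleepy. Section 10.5 lists a road traffic collision, or a blood pressure rise needing treatment or admission, as events that would be unexpected. A CPAP-first participant leaves Visit 4 after seven sham nights, and no later contact is planned. An event on that journey or the next day would reach the team only by chance. The oversight review in section 10.4 and the ethics committee report in section 10.6 can act only on events that reach the team.

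The same rule leaves people without a Visit 4 with no closing date, although some of them have been exposed to withdrawal.

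**Working it through.** The protocol states no figure for follow-up after withdrawal, so there is none to reproduce. The calculation is calendar arithmetic on its own schedule.

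**Inputs**
- Each treatment period: 7 days, Visit 1 to 2 and Visit 3 to 4 (section 9.8).
- Washout on own CPAP: at least 14 days (section 9.8).
- End of SAE collection: the participant's Visit 4 (section 10).
- Outer limit: 18 weeks = 126 days from the start of screening (section 7).
- Screening: 7 nights, the last 4 off CPAP, then at least 14 days back on CPAP before randomisation (section 9.3).
- Numbers: up to 30 randomised, with recruitment stopping at 22 evaluable completers (section 11.3); simple randomisation (section 9.4).

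**Observation after the sham week** = date of Visit 4 minus date on which the sham week ends.
- Sham-first: sham ends at Visit 2, so at least 14 + 7 = 21 days. The longest possible, with earlier intervals at their minimum, is 126 − (7 + 14 + 7) = 98 days.
- CPAP-first: sham ends at Visit 4, so 0 days.

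**Number affected.** Section 9.4 states no allocation ratio. Assuming equal allocation, the expected number in CPAP-first is 22/2 = 11 if hardly anyone drops out and 30/2 = 15 if all 30 are randomised. Simple randomisation can move the actual split away from half.

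**Screening withdrawal.** For randomised participants the four nights off CPAP are well covered. In CPAP-first they are followed by at least 14 + 7 + 14 = 35 days inside the window before the sham week starts.

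**People without a Visit 4**

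| Group | Exposed to withdrawal? | Start of SAE collection | End of SAE collection |
|---|---|---|---|
| Fail on HbA1c | No: told before CPAP is stopped (9.3) | Screening Visit | Not stated |
| Fail after four nights off CPAP | Yes | Screening Visit | Not stated |
| Randomised, stop early because of an AE | Yes | Screening Visit | Not stated; that AE is followed until resolved or stable (9.10) |
| Randomised, stop early for another reason | Yes | Screening Visit | Not stated |

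**The case against.** The case on the other side is that section 10 is explicit for completers and nothing else in the protocol contradicts it. All seven sham nights are inside the window in both sequences. Any crossover that ends at its last visit observes the second period for less time than the first. Safety is not among the objectives in section 6, and no comparison of SAEs by sequence is planned. Section 10.5 reports no SAEs in over 100 participants of earlier, longer withdrawal studies, so few events should be expected.

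Most of that stands, and it limits the weight of the point. It does not remove the gap. Zero events in 100 still leaves a one-sided 95% upper bound of 1 − 0.05^(1/100) = 0.0295, about 3%. The protocol does not say how long those earlier participants were observed after withdrawal.

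A reader might also infer several stronger things that the protocol does not support:
- *SAEs ongoing at Visit 4 are abandoned.* Section 10 limits when an SAE must occur, not how long a reported one is followed, and section 10.4 accepts follow-up information without a cut-off.
- *Screen failures have no safety window at all.* The start is defined; only the end is missing.
- *CPAP-first participants are never observed after any withdrawal.* They are observed after the screening withdrawal; the zero applies to the sham week.
- *About half of withdrawal-related SAEs will be missed.* That would need the events to appear only after sham ends, for which the protocol gives no evidence.
- *The earlier trials' zero count is undermined.* It does not depend on this trial's window.
- *The day of Visit 4 is excluded.* The text does not say whether that day counts, so this is an ambiguity.

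**Conclusion.** The point holds as a gap in safety capture. Followed exactly, section 10 gives 0 days of SAE observation after the sham week in the CPAP-first sequence and at least 21 days in the sham-first sequence. About 11 to 15 participants, roughly half of the randomised sham exposures, are affected, on the assumption of equal allocation and a total between 22 and 30. The day counts need no assumption beyond the protocol's own schedule. In addition, screen failures exposed to four nights off CPAP, and participants who stop early for reasons other than an adverse event, have no stated end of collection.

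The consequence is less complete safety data, by an amount that the protocol does not allow one to estimate and that is probably small. It is tempting to read the unequal follow-up as a bias in the trial result. It is not one: the glucose outcomes come from days and nights 5 to 7 of each period and are untouched by when SAE collection closes. The change is worth making because it is cheap and because the present rule stops looking before effective treatment resumes.

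**What to change.** Amend section 10 so that the end of SAE collection is set by exposure. Use one fixed interval after the last sham or off-CPAP night, the same for both sequences, for screen failures who came off CPAP, and for participants who discontinue early, as far as their chosen level of consent withdrawal in section 9.10 allows contact. Close it with one phone call. The length is for the sponsor to set; the 14-day back-on-CPAP interval already in the protocol is one example. In sham-first, an interval of up to 21 days has already passed by Visit 4. Collection to Visit 4 should be kept there so that the change loses nothing now captured. State in the same sentence that the day of Visit 4 is included.

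Align section 9.8, which now says that "participants' involvement in the study will end" at Visit 4, and the end-of-study definition in section 9.11, so that the closing call falls within the study.

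The cost is at most one call per participant and a later last-patient-out date, by about two weeks if the 14-day example is used. No visit, sample or analysis changes.

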10.1. Definition of Serious Adverse Events

A serious adverse event is any untoward medical occurrence that:

- results in death
- is life-threatening
- requires inpatient hospitalisation or prolongation of existing hospitalisation
- results in persistent or significant disability/incapacity
- consists of a congenital anomaly or birth defect.

Other 'important medical events' may also be considered a serious adverse event when, based upon appropriate medical judgement, the event may jeopardise the participant and may require medical or surgical intervention to prevent one of the outcomes listed above.

NOTE: The term "life-threatening" in the definition of "serious" refers to an event in which the participant was at risk of death at the time of the event; it does not refer to an event which hypothetically might have caused death if it were more severe.

10.2. Assessment results outside of normal parameters as SAEs

Abnormal blood results will only be reported as SAEs if thought to be clinically significant and to require ongoing management or treatment. Abnormal blood glucose results (fasting glucose levels or HbA1c levels) will not be reported as SAEs even if clinically significant as this data will be captured in the primary and secondary outcome data. Any abnormal blood results will be treated/managed as appropriate by the trial clinician and the participants GP will be informed when appropriate.

10.3. Assessment of Causality

The relationship of each adverse event to the trial medication must be determined by a medically qualified individual according to the following definitions:

Unrelated – Where an event is not considered to be related to the intervention

Possibly Related – although a relationship to the intervention cannot be completely ruled out, the nature of the event, the underlying disease, concomitant medication or temporal relationship make other explanations possible.

Probably Related – the temporal relationship and absence of a more likely explanation suggest the event could be related to the intervention

Definitely Related – the known effects of the IMP, its therapeutic class or based on challenge testing suggests that the intervention is the most likely cause.

All SAEs labelled possibly, probably or definitely related will be considered as related to the intervention.

10.4. Reporting Procedures for Serious Adverse Events

All SAEs will be reported to ORTU using the ORTU SAE Reporting Form. The Site Study Team will report to ORTU as soon as possible after becoming aware of the event being defined as serious. ORTU will perform an initial check of the report, request any additional information, and ensure a nominated Medical Reviewer provide a review. It will also be reviewed at the next Trial Safety Oversight Group meeting. All SAE information must be recorded on an SAE form and scanned and emailed, to ORTU [contact].

Additional and further requested information (follow-up or corrections to the original case) will be detailed on a new SAE Report Form and scanned/emailed to ORTU.

The ORTU Safety Oversight Group will review all SAEs for the study reported during the reporting period and cumulatively. The aims of this committee include:

- To pick up any trends, such as increases in un/expected events, and take appropriate action
- To seek additional advice or information from investigators where required
- To evaluate the risk of the trial continuing and take appropriate action where necessary

10.5. Expectedness

As the trial intervention, CPAP withdrawal is not an IMP, there is no separate IMP brochure. The only expected AEs are:

- Daytime sleepiness
- Rise in blood pressure (average expected, 9 mmHg)

Depending on the severity of these events they may become unexpected. For example, it is expected that participants may experience excessive daytime sleepiness or hypertension. It is not expected that daytime sleepiness will lead to road traffic collisions or that the rise in blood pressure will require treatment or hospitalisation. In previous CPAP withdrawal studies, with a similar but longer CPAP-withdrawal periods, there have been no serious adverse events in over 100 participants.

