8.3. Exclusion Criteria

The participant may not enter the trial if ANY of the following apply:

- Diabetes mellitus requiring treatment with regular insulin therapy.
- Previous ventilatory failure (awake resting arterial oxygen saturation <93% or known arterial $PCO_2 > 6kPa$) or severe respiratory disorders other than OSA.
- Unstable, untreated coronary or peripheral artery disease, severe arterial hypertension (>180/110mmHg), severe arterial hypotension (<90/60mmHg).
- Poorly controlled diabetes with HbA1c ≥10.0% (86mmol/mol).
- Unstable diabetic retinopathy requiring or currently undergoing specialist treatment.
- Previously diagnosed with Cheyne-Stokes breathing.
- Current professional driver or vigilance critical occupation.
- Any sleep-related accident.
- Mental or physical disability precluding informed consent or compliance with the protocol.
- Non-feasible trial follow-up (for example, distance from follow-up centre, physical inability).

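### Section 10 records and reviews only serious adverse events, so the two escalations that section 10.5 itself names, a collision and a blood pressure rise needing treatment, have no required route when they are non-serious

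*Protocol*

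**What the plan says.** The opening of section 10 sets the scope, from the screening visit to Visit 4: "Safety data will be collected as described below for serious adverse events". Section 10.4 keeps to it for reporting, "All SAEs will be reported to ORTU using the ORTU SAE Reporting Form", and for review, "The ORTU Safety Oversight Group will review all SAEs for the study reported during the reporting period and cumulatively". One stated aim of that review is "To pick up any trends, such as increases in un/expected events, and take appropriate action". Section 10.6 sends only related and unexpected SAEs to the ethics committee.

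Section 10.5 lists daytime sleepiness and a rise in blood pressure as the only expected adverse events, and then adds "Depending on the severity of these events they may become unexpected". Its examples follow: "It is not expected that daytime sleepiness will lead to road traffic collisions or that the rise in blood pressure will require treatment", with hospital admission completing the sentence. Section 10.3 uses wider language on causality: "The relationship of each adverse event to the trial medication must be determined by a medically qualified individual".

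At entry, section 8.3 excludes anyone with "Any sleep-related accident".

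**The concern.** Section 10.5 moves an event from expected to unexpected by its severity. Every step that would bring the event to anyone's notice is instead triggered by seriousness. These are different scales: a collision can be alarming and informative without an admission, and a blood pressure rise can lead to a new prescription without meeting any fixed criterion in section 10.1.

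What is at stake is whether the harms that the protocol singles out can be seen and reported. Each participant who completes the trial has CPAP withdrawn twice, for 4 nights at screening and 7 nights on sham, 11 nights in all. If one of these events occurs in non-serious form, the Safety Oversight Group may not hear of it, and the final report may be unable to say how often it happened on sham and how often on CPAP.

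**Working it through.** No arithmetic applies. The question is which events the safety system is required to capture, so the check follows the named events through it.

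**Scope of each step**

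| Step | Protocol section | Covers |
|---|---|---|
| Collection | 10 (opening) | SAEs |
| Report to ORTU | 10.4 | SAEs |
| Oversight review | 10.4 | SAEs |
| Report to ethics committee | 10.6 | Related and unexpected SAEs |
| Causality | 10.3 | Worded for every adverse event; its closing sentence speaks of SAEs |
| Follow-up after withdrawal | 9.10 | Any adverse event that causes withdrawal |

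**Seriousness (section 10.1).** There are five fixed criteria: death, threat to life, admission or prolonged admission, lasting or significant disability, and congenital anomaly. A further clause allows other important medical events to be counted, on medical judgement. Of the outcomes named in section 10.5, only admission is itself a fixed criterion.

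**Tracing the two escalations**

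1. *A collision without death, threat to life, admission or disability.* It meets no fixed criterion. It enters the system only if someone judges it an important medical event. If the participant withdraws because of it, section 9.10 provides follow-up and a CRF entry of the reason, if known. If the participant carries on, no visit procedure asks about it.
2. *A blood pressure rise treated without admission.* The same two routes apply. Triplicate clinic readings at Visits 1 to 4 (sections 9.7 and 9.8) would show a rise that is present at a visit, but not that treatment was started. Medications are reviewed at screening (section 9.3). Section 12.1 mentions concurrent medication as something that may be summarised from hospital records, but no later visit is assigned to ask about it.

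**What is already covered**

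- The two expected events themselves are measured: blood pressure and the Epworth score at Visits 1 to 4.
- Eligibility is rechecked at Visit 1, after the screening withdrawal, and a sleep-related accident is one of the exclusions.
- Section 9.10 allows discontinuation for ineligibility that arises during the trial. The schedule in section 9 marks eligibility assessment only at screening and Visit 1.

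What remains uncovered is the non-serious collision or other sleep-related accident after Visit 1, and blood pressure treatment started or changed at any time after screening.

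**The case against.** The strongest reply is that section 10.5 never promised to collect adverse events. Expectedness serves to decide which SAEs go to the ethics committee, so the section may only be warning that a serious sleepiness or blood pressure event is not automatically expected. On that reading it sits comfortably with SAE-only collection, which is a reasonable choice for a small study of 7 nights' withdrawal with no medicinal product. The trend-spotting aim in section 10.4 directly follows the sentence on reviewing SAEs and can be read as trends among them. The causality wording in section 10.3 stands beside template terms about trial medication and ends on SAEs, so it may be loose drafting. Collision risk is also reduced at entry: professional drivers are excluded, and section 16.4 has participants told not to drive when sleepy. The CRF and the data management and monitoring plans are not in view and may ask more than the protocol shows.

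Much of this stands. The wording of sections 10.3 and 10.4 is something to tidy, not proof of failed monitoring, and SAE-only collection is not wrong in itself. What it does not answer is that the protocol names particular harms and then requires no one to ask about them. The important-medical-event clause is open but optional, and section 10.5 does not tie its examples to it.

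Three stronger readings are not supported:

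- A reader might infer that the named harms go wholly unmonitored or cannot be compared by arm. That is untrue of blood pressure and sleepiness, which are measured in each arm.
- A reader might infer that someone who has an accident on sham in the first period is exposed to sham again. In this crossover that participant moves to CPAP.
- A reader might use the absence of SAEs in over 100 earlier participants to argue that SAE review carries little information in a trial of 30. Such a calculation concerns SAEs and says nothing about the events that could be missed.

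**Conclusion.** The point holds in limited form. Non-serious collisions and outpatient blood pressure treatment, both of a kind that section 10.5 treats as unexpected, have no required route into safety collection, oversight review or tabulation by arm. They appear only through a discretionary judgement or a withdrawal.

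The number of events at issue is unknown. The protocol gives no rate for them, and its reassurance from earlier withdrawal studies covers SAEs only. The conclusion rests on the protocol text and assumes that the unseen CRF and supporting plans do not already ask these questions. It does not mean that withdrawal is unsafe, or that the primary glucose analysis is affected. This is a low-cost improvement to participant safety and to reporting, not a flaw that undermines the trial.

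**What to change.** In section 10, state that the escalations named in section 10.5 are handled as follows, whatever their seriousness:

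- Ask at Visits 1 to 4 about any road traffic collision or other sleep-related accident, and about blood pressure treatment started or changed. Visit 1 then also captures the screening withdrawal.
- Send positive answers to ORTU, and have the Safety Oversight Group review them with the SAEs.
- Tabulate those from the randomised periods by arm.

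Reconcile section 10.3 with the opening of section 10, so that causality is required for the events that are actually collected, and state in section 10.4 which events the trend review covers. No new blood pressure threshold or clinical rule is needed. Early stopping of sham needs no separate question, because the study machine records nightly use and is downloaded at Visits 2 and 4.

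The cost is a few yes/no questions at visits that already take place, a few extra report forms and a protocol amendment.
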